9.1 Sample Size and Stopping Rules for Primary Outcome

The primary outcome is intention-to-treat 90-day all cause in-hospital mortality, where in-hospital includes both study and discharge hospitals (i.e. transfer hospitals or LTAC). Subjects who are discharged home (defined as residence prior to admission) prior to day 90 will be assumed to be alive at day 90.

Sample size is based on a comparison of binomial proportions with an overall two-sided alpha level of 0.05 and power of 0.90. With 15% mortality rate in liberal fluid group and 10.5% mortality rate in the restrictive group, maximum required total sample size is 2320 subjects.

The presumed 15% mortality rate in the liberal fluid group is based on several recently published clinical trials (Process [2], ARISE [3], Promise [4]).

This trial will stop for efficacy of either the restrictive or liberal fluid strategy arm, or futility. The study is designed with a symmetric group sequential t^4 alpha error spending function and a symmetric non-binding t^4 beta error spending function, where t is the information time, defined as the ratio of the effective sample size at the time of the look to the eventual sample size.

We plan to have two interim analyses and one final analysis that will be approximately evenly spaced. However, the scheduling of the DSMB meetings may alter this schedule.

Tables 1 and 2 present the stopping boundaries at each of the two interim analyses if they are equally spaced. The tables present stopping boundaries as either a one-sided p-value or an observed mortality difference. Table 3 presents the probability of stopping at each stage under the null (no effect of fluid) and alternative (restrictive fluid reduces mortality from 15% to 10.5%) hypotheses respectively.

Table 1. Stopping Boundaries: One Sided P Values

Stage	Sample Size	Lower Efficacy	Lower Futility	Upper Futility	Upper Efficacy
1	773	0.0003086	.	.	0.99969
2	1547	0.00479	0.27413	0.72587	0.99521
3	2320	0.02361	0.02361	0.97639	0.97639

Table 2. Stopping Boundaries: Mortality Differences

Stage	Sample Size	Lower Efficacy	Lower Futility	Upper Futility	Upper Efficacy
1	773	-0.08194	.	.	0.08194
2	1547	-0.04384	-0.01016	0.01016	0.04384
3	2320	-0.02742	-0.02742	0.02742	0.02742

Table 3. Cumulative Stopping Probabilities

Stage	Stop: Reject Null Given Null	Stop: Accept Null Given Null	Stop: Reject Null Given Alternative	Stop: Accept Null Given Alternative
1	0.00062	0.00000	0.06136	0.00000
2	0.00988	0.45174	0.52878	0.01919

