12.5. Withdrawal of Consent

Patients or the LAR may withdraw or be withdrawn (by the LAR) from the trial at any time without prejudice. Data recorded up to the point of withdrawal will be included in the trial analysis, unless consent to use their data has also been explicitly withdrawn. If a patient or LAR requests termination of study procedures during the treatment period, the procedures will be stopped but the patient will continue to be followed up as part of the trial. If a patient or LAR withdraws consent during trial treatment, the study procedures will be stopped but permission will be sought to access medical records for data related to the trial. If a patient or LAR wishes to withdraw from the trial after completion of trial treatment, permission to access medical records for trial data will be assumed unless explicitly withdrawn.

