## **2. Endpoints**

### **2.1 Primary Outcome**

The primary outcome is all-cause mortality prior to discharge home before day 90. "Home" is defined as a patient's place of residence prior to enrollment. Thus, if a patient is discharged to a location that is different from the place of residence prior to enrollment (e.g. rehabilitation facility or hospice) then the patient will be followed until they return to their original location, 90 days, or death, whichever comes first.

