#### 5. Statistical Methods

##### Primary Outcome

The primary outcome is intention-to-treat 90-day all cause in-hospital mortality, where in-hospital includes both study and discharge hospitals (i.e. transfer hospitals or LTAC). Subjects who are discharged home (defined as residence prior to admission) prior to day 90 will be assumed to be alive at day 90. Analysis of the primary outcome will be based on the Kaplan Meier day 90 mortality point estimates with all patients who are discharged home or still alive at day 90 censored at day 91, which is beyond the last possible day of death. The day 90 mortality estimates in the two treatment groups will be compared by a Z-test using Greenwood's standard error (Kalbfleisch, J. D. and Prentice, R. L. (1980), *The Statistical Analysis of Failure Time Data*, New York: John Wiley & Sons.).

If there is no loss to follow up then the primary outcome will be compared between treatment groups on the risk difference scale using a generalized linear model with a binomial distribution function and identity link function.

The hypothesis regarding the primary outcome is a two-sided superiority hypothesis.

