### Missing Data

Analysis is based on all available data with no imputation of missing data; except in the case of selected derived variables, for example SOFA variables.-

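### When patients are lost while still in a facility, the SAP's Kaplan-Meier rule for the primary outcome slightly understates mortality; a competing-risk estimator on the same data would avoid this

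*SAP*

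**What the plan says.** The primary outcome is death before discharge home, up to day 90. SAP section 2.1 says that a patient discharged elsewhere than home "then the patient will be followed until they return to their original location, 90 days, or death, whichever comes first". SAP section 5 adds: "Subjects who are discharged home (defined as residence prior to admission) prior to day 90 will be assumed to be alive at day 90".

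The estimator is the Kaplan-Meier day-90 value, "with all patients who are discharged home or still alive at day 90 censored at day 91". The arms "will be compared by a Z-test using Greenwood's standard error". There is one alternative: "If there is no loss to follow up then the primary outcome will be compared between treatment groups on the risk difference scale", by a binomial model with identity link.

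Two other rules bear on incomplete follow-up. SAP section 5, Missing Data: "Analysis is based on all available data with no imputation of missing data", apart from selected derived variables. Protocol 12.5: "Data recorded up to the point of withdrawal will be included in the trial analysis", unless use of the data is also refused. The SAP does not say when a patient lost in a facility is censored; last contact is the natural reading.

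For the interim looks, Protocol 9.1 gives information time as "defined as the ratio of the effective sample size at the time of the look to the eventual sample size". Neither document names an interim estimator, a competing-risk method, a sensitivity analysis for the primary outcome or an expected loss rate.

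**The concern.** Once home, a patient's primary outcome is settled as alive. Only patients still in a facility can be censored before day 90. Kaplan-Meier gives each of them the average later hazard of everyone still in the risk set, and under the SAP rule that set includes every patient already home, whose hazard is zero by definition. Censoring therefore depends on a known state, facility or home, that also determines risk.

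The binomial model takes over when nobody is lost, so Kaplan-Meier is in use only where this can happen. At stake are a small downward bias in each arm's mortality and, if in-facility loss or discharge timing differs by arm in this non-blinded trial, a small shift in the treatment difference.

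**Working it through.** **1. The plan's own figure.** Inputs from Protocol 9.1: 15% versus 10.5%, two-sided alpha 0.05, power 0.90. The mean rate is 0.1275.

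n per arm = [1.960 × √(2 × 0.1275 × 0.8725) + 1.2816 × √(0.15 × 0.85 + 0.105 × 0.895)]² / 0.045² ≈ 1153, or 2306 in total, against 2320 stated. Simulating the three-stage design from the Table 1 boundaries gives a null rejection rate of 0.0491 (stated 0.04922) and power of 0.897 (stated 0.89765).

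The final boundary is 2.742 points (Table 2) at one-sided p 0.02361 (Table 1), for which z = 1.984. The standard error of the difference is thus 2.742 / 1.984 ≈ 1.38 points.

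**2. No early censoring.** The SAP estimate is 1 − Π(1 − d/n), where n counts everyone not yet dead, at home or in a facility. The product telescopes to deaths divided by patients, so the rule is exact.

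**3. Hand example (invented numbers, to show the mechanism).** Of 100 patients, 10 die on day 5 and 60 go home on day 8. Of the 30 left in a facility, 10 are lost on day 10. Of the other 20, 5 die on day 30.
- SAP Kaplan-Meier: 1 − 0.90 × (1 − 5/80) = 15.6%.
- Aalen-Johansen: 0.10 + 0.30 × 5/20 = 17.5%.

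The lost patients are given a later risk of 5/80 = 6.25%, where comparable in-facility patients had 5/20 = 25%.

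**4. Size per arm.** The documents give neither loss rates nor lengths of stay, so both are assumed. Kaplan-Meier bias in percentage points, 2 million simulated patients per scenario, median 10 days to discharge home:

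| Lost in a facility | 15% arm, lost days 10–60 | 10.5% arm, lost days 10–60 | 15% arm, lost days 1–30 | 10.5% arm, lost days 1–30 |
|---|---|---|---|---|
| 1% | −0.14 | −0.07 | −0.07 | −0.02 |
| 2% | −0.21 | −0.20 | −0.17 | −0.09 |
| 3% | −0.36 | −0.28 | −0.22 | −0.15 |
| 4% | −0.51 | −0.36 | −0.23 | −0.21 |

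That is 0.02 to 0.14 points per 1% lost, and 0.21 to 0.51 points at 4%. A second simulation (1 million patients per scenario, three other stay patterns) agrees: for a true 15%, about 0.05 to 0.2 points at 1–2.4% loss and 0.2 to 0.5 at 3–7%.

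**5. Effect on the arm difference.**
- Equal 1% loss: 0.14 − 0.07 = 0.07 or 0.07 − 0.02 = 0.05 points. Equal 4% loss: 0.51 − 0.36 = 0.15 or 0.23 − 0.21 = 0.02 points.
- Power under equal loss (second simulation, 70%/30% mix of mean stays of 7 and 35 days, fixed-sample formula with 1160 per arm): 0.90 with no loss. At 1.5% loss the difference is 14.82 − 10.40 = 4.42 points and power 0.89. At 4.3% it is 14.55 − 10.20 = 4.35 points and power 0.89.
- Loss of 4% in one arm and 1% in the other: from 0.21 − 0.07 = 0.14 to 0.51 − 0.07 = 0.44 points, which is 3% to 10% of 4.5. The largest is 0.44 / 1.38 ≈ 0.3 standard errors. More loss in the 15% arm shrinks the difference; more loss in the 10.5% arm enlarges it.
- No true effect, loss of 1.5% versus 4.3%: 14.86 − 14.59 = 0.27 points, against the final boundary of 2.74.

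**6. Interim looks, if they use this estimator.** At 50 patients a month (Protocol 8.1), the bias at look 1 under the step 4 assumptions is −0.22 and −0.18 points, or 0.04 on the difference. Across the second simulation's stay patterns, and up to 2320/36 ≈ 64 patients a month (three-year enrolment, Protocol Appendix J), the largest biases are 15.01 − 14.49 = 0.52 and 10.49 − 10.13 = 0.36, or 0.16 on the difference. The look-1 efficacy boundary is 8.19 points.

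**The case against.** The strongest reply is that the rule suits the estimand and that loss should be rare. Home-discharged patients count as alive at day 90, so keeping them at risk is right, and step 2 shows no bias under complete follow-up. In-facility patients are followed to home, death or day 90. Vital status is also sought by telephone, records, public sources and the national death index (SAP section 2.2, item 11), and a patient confirmed alive at day 90 is event-free. Protocol 12.5 continues follow-up when only study procedures are stopped. All of this stands, with one gap: a death found in an index does not show whether the patient had first gone home.

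A second reply is that the support for Aalen-Johansen is partly circular. It stayed within 0.04 to 0.05 points of the true rate because simulated loss was unrelated to prognosis among in-facility patients, which is its own assumption. If lost patients were at much lower risk than others in a facility, the Kaplan-Meier bias could shrink or reverse. This also stands, and it is why the fix needs a sensitivity analysis.

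A reader might go further and infer that the primary estimate is biased in any event, that the type I error is at risk, or that the interim decisions are compromised. The documents do not support these readings. The bias needs in-facility loss, whose rate is not given. With equal censoring and no effect, the two arms' biases cancel. The wording on effective sample size defines information time; it suggests an estimator for partial follow-up but does not state one.

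**Conclusion.** The point holds as a free improvement. Whenever Kaplan-Meier rather than the binomial model is in use, patients lost in a facility receive a diluted hazard. If they resemble others still in a facility, mortality is understated by about 0.02 to 0.14 points per 1% lost. Equal loss slightly attenuates the difference. Even the assumed 4% versus 1% imbalance moves it by at most about 0.3 standard errors. At look 1, if the estimator applies there, the bias is about 0.2 points per arm but only about 0.04 on the difference (up to 0.16 under the longest stays assumed). The mechanism and the exactness under complete follow-up follow from the SAP text alone. Every magnitude rests on assumed loss rates, loss times and stay patterns.

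**What to change.** In SAP section 5, estimate the day-90 cumulative incidence of death before discharge home by Aalen-Johansen, with discharge home as a competing event and patients lost in a facility censored at last contact. Compare the arms by a Z-test with the corresponding variance. State that this applies at the final analysis and at any interim look with incomplete follow-up. With complete follow-up the estimate equals the planned simple proportion.

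Add a sensitivity analysis for patients lost in a facility, for example all alive and then all dead. This matters more than the choice of estimator. In the 1.5% loss scenario of step 5, all-alive gives 14.7% and all-dead about 14.7 + 1.5 = 16.2%, a band of 1.5 points, while the two estimators differ by 14.96 − 14.82 = 0.14 points.

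The cost is a few sentences in the SAP and standard software. No new data are needed.

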4.7 Randomization

After obtaining a signed and dated informed consent from the subject or the subject's legal authorized representative (LAR), we will randomize subjects via the coordinating center web based randomization system. Each research coordinator will have a unique Personal Identification Number (PIN) to access the randomization system. Each subject will receive a computer-generated study ID number and study arm assignment to either the restrictive or liberal treatment arm. An emailed confirmation will be sent to the study site. Randomization will be stratified by the enrolling institution.

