7.1 Background Assessments

The following information will be collected from information available prior to randomization. If more than one value is available in the 24 hours prior to randomization, the value closest to the time of randomization will be recorded. If no values are available from the 24 hours prior to randomization, then values will be measured up to 24 hours. All values will be derived from clinically available data. (see Time of Events Schedule in Appendix F)

1. Demographic and Admission Data (including age, sex, race)
2. Pertinent Medical History and Physical Examination (including components of the Charlson co-morbidity score)
3. Height; gender; measured Body Weight (mBW); calculated predicted body weight (PBW); body mass index (BMI)
4. Location when inclusion criteria met: ED, ward, ICU, referring hospital
5. Vital signs: heart rate (beats / min), systemic systolic and diastolic BP (mmHg), body temperature (^oC), and oxygen saturation with FiO₂
6. Clinical laboratory testing results
7. Presumed site of infection
8. SOFA Score: as described in Appendix C
9. Attending physician assessment of CLOVERS eligibility (Appendix I)

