9.3 Effect of Change in Fluid Protocol on Outcome

The initial two-liter fluid infusion in the liberal fluid treatment group was modified to a one-liter fluid infusion followed by an optional additional liter at the treating physician's discretion. To understand the potential impact of this change in the liberal fluid treatment strategy on the primary outcome we will do an interaction analysis which will be presented as shown in the following table.

Table 5: All-Cause Mortality Prior to Discharge Home Before Day 90
Stratified by Liberal Fluid Treatment Epoch

Epoch	Liberal Fluid Group	Restrictive Fluid Group	Difference (95% CI)	P-value
Two-Liter Fluid Infusion Epoch	0.xxx±0.xxx	0.xxx±0.xxx	0.xxx (0.xxx, 0.xxx)	0.xxx
One-Liter Fluid Infusion Epoch	0.xxx±0.xxx	0.xxx±0.xxx	0.xxx (0.xxx, 0.xxx)	0.xxx
Interaction			0.xxx (0.xxx, 0.xxx)	0.xxx

The primary outcome analysis will be still based on a two-way comparison of all participants randomized to liberal fluid and all those randomized to restrictive fluid unstratified by the two liberal fluid treatment epochs as shown in the following table.

Table 6: All-Cause Mortality Prior to Discharge Home Before Day 90

Liberal Fluid Group	Restrictive Fluid Group	Difference (95% CI)	P-value
0.xxx±0.xxx	0.xxx±0.xxx	0.xxx (0.xxx, 0.xxx)	0.xxx

Interactions between the liberal and restrictive treatment groups and the two liberal fluid treatment epochs for study process metrics, such as intervention period fluid and vasopressor use, and selected secondary outcomes may also be reported as in Table 5 above.

10. Data Collection and Monitoring

Data Collection: The research coordinators will transfer data to the Clinical Coordinating Center on a prescribed basis through a secure web-based data collection program.

Investigators will use these reports to identify aspects of protocol management that can be improved at their Centers. The on-target performances of all centers will also be included, allowing investigators at each center to know how their center is performing relative to other PETAL Centers. On-target performances will be discussed during regular meetings of the Steering Committee. The Institutional Support Committee will provide advice and assistance to Centers that are not performing up to expectations. On-target data for the specific variables according to study group will be included in the primary reports of the results of the individual trials.

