**10. Change in SOFA score between baseline and 72 hours**

We will calculate the SOFA score upon enrollment and at 72 hours using clinically available data. If a value is not available at baseline, it will be assumed to be normal. At the 72 hours assessment, if a value is missing then we will carry forward the closest previously known value. If a patient is intubated or heavily sedated at either 0 or 72 hours, the GCS will be omitted when calculating the change in score. If a patient was on renal replacement therapy prior to presentation, then the renal dysfunction component to the SOFA score will be omitted as well.

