#### 4. Baseline Characteristics

1. Demographics – Age, Gender, Ethnicity, Race
2. Primary source of infection
3. Co-Morbidities – Charlson, BMI, Pre-hospital level of care
4. Location at time of randomization
5. Illness severity – SOFA (Total and components), mechanical ventilation, ARDS, total pre-randomization fluid input, vasopressor use and infusion rate prior to and at randomization, vital signs, WBC, lactate

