### Secondary Analysis by Subgroups

The secondary analysis of the primary and secondary outcomes by subgroups will use the same methods as the primary except that the statistical models will be augmented with subgroup and subgroup by treatment interaction terms.

The analysis is intention to treat and significance testing will be two-tailed at  $\alpha = 0.05$  with no adjustment made for multiple comparisons.

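### No covariate-adjusted estimate of the primary mortality effect is planned, even as a sensitivity analysis; the planned test is valid, so what is lost is a modest amount of precision

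*SAP*

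**What the plan says.** - **Randomisation.** Protocol 4.7: "Randomization will be stratified by the enrolling institution".
- **Baseline data.** SAP section 4 lists age and, under illness severity, "SOFA (Total and components), mechanical ventilation, ARDS, total pre-randomization fluid input". Protocol 7.1 also collects age and SOFA.
- **Primary analysis.** SAP section 5 takes the Kaplan-Meier day-90 mortality in each arm with Greenwood's standard error: "The day 90 mortality estimates in the two treatment groups will be compared by a Z-test". If nobody is lost to follow-up, it uses a binomial model with identity link instead. Neither branch names site or any other covariate. Protocol 9.3 agrees: "The primary outcome analysis will be still based on a two-way comparison of all participants".
- **Models with added terms.** For subgroups, including age over 65 and SOFA quartile, "the statistical models will be augmented with subgroup and subgroup by treatment interaction terms". Protocol 9.3 plans an interaction with liberal-fluid epoch. These models show whether the effect varies; they do not give an adjusted overall effect.
- **Baseline SOFA.** SAP 2.2 item 10: "If a value is not available at baseline, it will be assumed to be normal". Protocol 7.1 first restricts background data to what is available before randomisation, then adds: "If no values are available from the 24 hours prior to randomization, then values will be measured up to 24 hours".
- **Change in SOFA.** SAP section 5 assigns continuous secondary outcomes a t-test. Under SAP 2.2 item 10, "If a patient is intubated or heavily sedated at either 0 or 72 hours, the GCS will be omitted" from the change.

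**The concern.** The trial collects baseline variables that can be expected to predict death and uses them to define subgroups, but never to sharpen the main estimate. The one stratification factor is also absent from the analysis. If the result falls near the final boundary, readers will ask whether one arm was older or sicker. The SAP has no pre-specified adjusted estimate to set beside the primary one, and a covariate set chosen after unblinding would carry less weight.

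Two related gaps appear once SOFA is considered as a covariate. It is unclear whether a baseline SOFA value may date from after randomisation. And change in SOFA is itself compared without using the baseline score.

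**Working it through.** **1. The plan's own figures.** Inputs from protocol 9.1: mortality 15% and 10.5%, two-sided alpha 0.05, power 0.90, N = 2320 (1160 per arm), two interim looks.
- Fixed-design two-proportion formula, pooled variance: 1153 per arm, 2306 in total, against 2320 stated.
- Simulating the Table 1 boundaries with 2 million paths: power 0.898 (Table 3: 0.89765) and type I error 0.0489 (Table 3: 0.04922).

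The sample size was derived for an unadjusted comparison, and that comparison delivers it.

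**2. Validity under site stratification.** The unadjusted test was simulated with 50 sites (the planning number in protocol 8.1), blocks of 4 (assumed) and assumed site and covariate effects. It rejected 4.7% to 5.6% of the time under the null (Monte Carlo SE about 0.4 points). This is consistent with 5%.

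**3. Precision of the planned estimate.** SE = sqrt[(0.15 × 0.85 + 0.105 × 0.895)/1160] = 0.01382. The 95% half-width is 1.96 × 0.01382 = 2.71 points.

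**4. Precision with adjustment.** No c-statistic or R² is given, so a range is assumed. Risk follows a logistic-normal model with mean (15% + 10.5%)/2 = 12.75%. R² is the variance of the predicted risk divided by 0.1275 × 0.8725. Adjusted half-width = 1.96 × SE × sqrt(1 − R²). Chance imbalance in prognosis (95% range) = 1.96 × SE × sqrt(R²).

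| Assumed c-statistic | SD of linear predictor | R² | Adjusted half-width (points) | Chance imbalance, ± (points) |
|---|---|---|---|---|
| 0.60 | 0.362 | 1.5% | 2.69 | 0.33 |
| 0.65 | 0.556 | 3.4% | 2.66 | 0.50 |
| 0.70 | 0.768 | 6.5% | 2.62 | 0.69 |
| 0.75 | 1.012 | 10.9% | 2.56 | 0.89 |
| 0.80 | 1.308 | 16.8% | 2.47 | 1.11 |

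The last two columns add in quadrature to the planned half-width. At 0.70, sqrt(2.62² + 0.69²) = 2.71. The imbalance is therefore already part of the unadjusted standard error.

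Site alone, with an assumed between-site SD of 0.2 to 0.5 on the logit scale, has R² of only 0.4% to 2.8%.

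**5. Why the SOFA covariate must precede randomisation.** Assume that 10% to 20% of baseline SOFA values were taken after randomisation, with an arm shift of 0.5 to 1 point, SOFA SD 3 and an odds ratio for death of 1.2 per point. The adjusted difference is then biased by 0.10 to 0.41 points. At c 0.70 the half-width gain is 2.71 − 2.62 = 0.09 points, which is smaller than that bias.

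**6. Change in SOFA.** With equal SDs and baseline to 72-hour correlation ρ, the variance of the change is 2σ²(1 − ρ), and the ANCOVA residual variance is σ²(1 − ρ²). The ratio is (1 + ρ)/2: 0.65 at ρ = 0.3 and 0.85 at ρ = 0.7. If the covariate is a reduced SOFA that correlates k = 0.9 with the scored baseline total, and relates to the change only through that total, the ratio is 1 − k²(1 − ρ)/2: 0.72 and 0.88.

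**The case against.** The strongest reply is that this is a preference and not a defect. The test is valid, the sample size was built for it, and at c-statistics of 0.60 to 0.70 the half-width shrinks by only 0.02 to 0.09 points. As a sensitivity analysis, adjustment leaves trial power unchanged. All of that stands, and it limits the point to a low-cost improvement.

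A reader might infer four stronger things that the documents do not support:

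- **That omitting the stratification factor invalidates the test.** The error rate holds in step 2.
- **That chance imbalance threatens the result.** Setting 0.33 to 1.11 points against the final boundary of 2.74 points (protocol Table 2) suggests this. But the imbalance is already inside the standard error, and the boundary allows for it.
- **That the protocol permits post-randomisation baseline values.** Protocol 7.1 opens by limiting data to those available before randomisation. Its fallback sentence is ambiguous; it is not an open permission.
- **That the adjusted test should be primary.** On paper its power would be 0.902 to about 0.94 over the assumed range. But one such estimator (random site intercepts, weighting for losses) rejected slightly too often at the first-look boundary in its main simulated scenario: 0.00074 against a nominal 0.00062, Monte Carlo SE 0.00004. The site variance was there fixed at its true value, which a real analysis would have to estimate. A second scenario showed no inflation (0.00063, SE 0.00006). The documents also do not say whether an interim look has already used the unadjusted test.

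One practical objection also stands. Protocol 7.1 says that the value closest to randomisation is recorded, but not that its time is. Whether late SOFA values can be identified has to be checked.

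**Conclusion.** The point holds as a missed gain in precision, not as an error. No adjusted estimate of the overall mortality effect is planned in any role, although usable baseline data are collected. The benefit is a 95% half-width of 2.69 to 2.47 points in place of 2.71, plus a pre-specified answer to questions about imbalance. Its size rests wholly on the assumed c-statistics of 0.60 to 0.80, with age and SOFA supplying most of it. If these covariates had no prognostic value, nothing would be gained.

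For change in SOFA the proportional gain is larger, a variance reduction of about 15% to 35% with the full baseline score. It too rests on assumed values (ρ of 0.3 to 0.7, equal SDs), and it concerns a secondary outcome only.

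**What to change.** Before unblinding, amend the SAP as follows.

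1. **Section 5, primary outcome.** Keep the unadjusted Kaplan-Meier Z-test as primary and for all stopping boundaries. Add one supportive marginal day-90 risk difference, standardised from a model with treatment, age, baseline SOFA and site, with a robust standard error. Report it beside protocol Table 6. State that the unadjusted test governs if the two disagree. Specify in advance how small sites and patients lost before day 90 enter the model.
2. **Baseline SOFA as a covariate.** Use only values recorded before randomisation, with missing components set to normal as SAP 2.2 item 10 already does. Clarify the fallback sentence in protocol 7.1 to match, and confirm that the timing of recorded values can be verified.
3. **Change in SOFA.** Replace the t-test by ANCOVA on a pre-randomisation SOFA covariate that does not depend on 72-hour intubation or sedation, for example the non-neurological components for all patients. The rule that drops GCS uses 72-hour status, so the covariate should not follow it.

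**Cost.** SAP wording and slightly more programming. The sample size, the marginal risk-difference estimand and protocol Tables 1 and 2 do not change. No new data are needed if pre-randomisation SOFA values can be identified. The supportive estimate depends on a model and will occasionally disagree with the primary test: in simulation at c 0.70 with a true 4.5-point effect, the two differed on final significance in 3.6% of trials. The rule on which test governs is therefore needed.

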### **1.11 Sample Size/Interim Monitoring**

1. Randomization 1:1; two-sided alpha 0.05.  
A total of 2320 patients are needed to detect a 4.5% absolute mortality difference between treatment groups with 90% power assuming 15% mortality in the liberal fluids group. The principal analysis will be intent-to-treat, based upon randomization assignment.
2. There will be a protocol feasibility assessment phase at the approximately 100-patient mark, and then after approximately 100 enrolled patients are available after any protocol changes for 2 more evaluation assessments. Aggregate data blinded to outcomes will be used to assess patient accrual, treatment protocol compliance, and separation of intravenous fluid and/or vasopressor administration. Protocol adjustments may be made at each of these patient marks to optimize the protocol. The study may be halted during the feasibility assessment phase for failure to meet pre-specified stopping guidelines
3. Trial progress will be evaluated by an independent Data and Safety Monitoring Board (DSMB) to determine whether the study should stop for superiority of either the liberal or restrictive fluid strategies; or, for projected trial futility. (See Appendix B) There will be two interim analyses and a final analysis conducted when approximately each successive 1/3 of the patients have been enrolled.

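### SAP 5 does not carry over the protocol 9.1 stopping boundary, and neither document allows for sequential stopping in the reported primary estimate, 95% CI or p-value

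*SAP*

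**What the plan says.** Protocol 9.1 sets out a group-sequential design. "Sample size is based on a comparison of binomial proportions with an overall two-sided alpha level of 0.05 and power of 0.90". "The study is designed with a symmetric group sequential t^4 alpha error spending function", together with a "symmetric non-binding t^4 beta error spending function". "This trial will stop for efficacy of either the restrictive or liberal fluid strategy arm, or futility". Tables 1 to 3 give the boundaries and stopping probabilities for looks at 773, 1547 and 2320 patients. The final one-sided efficacy boundary is 0.02361. The section adds that DSMB scheduling may move the looks, and it presents Tables 1 and 2 as the equally spaced case.

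SAP 1.11 gives "Randomization 1:1; two-sided alpha 0.05", then describes two interim analyses and a final one, with stopping for superiority or futility. It points to an Appendix B. The protocol's Appendix B covers look timing and DSMB governance and contains no boundary.

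SAP 5, Primary Outcome, defines the Kaplan-Meier day 90 estimates and states: "The day 90 mortality estimates in the two treatment groups will be compared by a Z-test using" Greenwood's standard error. If there is no loss to follow-up, an identity-link binomial model is used instead. The hypothesis is described as two-sided superiority. The section gives no alpha, critical value or boundary and does not refer to protocol 9.1.

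Protocol 9.3, Table 6, is the shell for the primary result. It has a column opening "Difference (95% CI" and a p-value column, and does not say how either is computed.

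**The concern.** A statistician working from SAP 5 is given a test statistic but not the value to compare it with. The only level that the SAP attaches to the primary comparison is the 0.05 in 1.11, without the qualifier (overall) that protocol 9.1 uses. Suppose the trial runs to the end and the final two-sided p-value falls between 0.0472 and 0.05. An ordinary 95% CI would then exclude zero although the Table 1 boundary had not been crossed, and nothing in the SAP says which governs.

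The second gap is in estimation. A trial that stops early for efficacy does so because the observed difference is large, so the raw difference at that point overstates the true one on average, and the ordinary 95% CI loses coverage. Under the design alternative an early efficacy stop is slightly more likely than not, so the raw figure could well be the one published.

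**Working it through.** **Inputs.** From protocol 9.1: mortality 15% against 10.5%, 2320 patients, t^4 spending, looks at 773, 1547 and 2320. From SAP 1.11: 1:1 allocation, hence 1160 per arm.

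**1. Reproducing the plan's boundaries.** Alpha spent per side by information time t is 0.025 × t^4:
- t = 1/3: 0.000309
- t = 2/3: 0.004938
- t = 1: 0.025

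Solving for the boundaries by recursive numerical integration gives one-sided p of 0.000309, 0.00479 and 0.02361 (|Z| of 3.424, 2.591 and 1.984), matching Table 1. The final two-sided level is 2 × 0.02361 = 0.0472.

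The standard error of the difference at full size is √[(0.15×0.85 + 0.105×0.895)/1160] = √(0.221475/1160) = 0.01382. The boundary difference is |Z| × 0.01382/√t, which gives 0.0820, 0.0438 and 0.0274. Table 2 has 0.08194, 0.04384 and 0.02742.

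The drift at the alternative is 0.045/0.01382 = 3.257. Cumulative rejection is then 0.0613, 0.5289 and 0.8976 with futility followed; Table 3 has 0.06136, 0.52878 and 0.89765.

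**2. Type I error.**

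| Final critical value | Futility ignored | Futility followed |
|---|---|---|
| 1.984 (protocol 9.1) | 0.0500 | 0.0492 |
| 1.960 (ordinary 0.05) | 0.0527 | 0.0518 |

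The design therefore controls alpha as stated. If the boundary were overlooked at the last look, the excess is 0.0527 − 0.0500 = 0.0027. The final interval half-width is 1.960 × 0.01382 = 2.71 points, or 1.984 × 0.01382 = 2.74 points when matched to the boundary.

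**3. Estimation, true difference 4.5 points.** Sample paths were simulated under the Table 1 boundaries, taking the raw difference ± 1.96 SE at the stopping look.
- Efficacy stop at look 1: probability 0.0614, mean raw estimate 9.23 points.
- Efficacy stop at look 2: probability 0.4684, mean raw estimate 5.63 points.
- Either: (0.0614×9.23 + 0.4684×5.63)/(0.0614 + 0.4684) = 3.204/0.5298, about 6.0 points. Against 4.5 this is about a third too large.
- Mean over all trials: about 4.85 points.
- Coverage of the ordinary 95% CI over all trials: 92.9% to 93.0% if futility is followed, 93.9% if it is ignored.

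**4. Estimation, true difference 3.0 points (15% against 12%).**
- Efficacy stop at look 1: probability 0.0140, mean 9.26 points. At look 2: probability 0.1814, mean 5.39 points.
- Either: (0.0140×9.26 + 0.1814×5.39)/0.1954 = 1.107/0.1954, about 5.7 points, with probability about 20%.
- Coverage given that early stop: about 83% to 84%, depending on whether the SE uses 12% or 10.5% in the restrictive arm.
- Coverage over all trials: about 94%.

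The last two figures have different denominators. The shortfall is marked only in the fifth of trials that stop early for efficacy.

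**The case against.** A reader who sets SAP 5 beside Table 1 might infer that the plan ignores its interim looks, that the primary test is run at the wrong level, or that the overall type I error exceeds 0.05. The documents do not support this. Protocol 9.1 calls 0.05 the overall level, specifies the spending function and gives a boundary for every look, and those boundaries reproduce. SAP 1.11 acknowledges the looks and the stopping rules. SAP 5 writes a two-tailed 0.05 into its secondary, process, adverse event, on-study and subgroup analyses but not into the primary one, and Table 6 states no alpha. Naming a Z-test does not replace the boundary it is compared with. The excess in step 2 arises only if analysts disregard protocol 9.1.

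It is also fair to say that recomputing the boundary at the actual information is already implied by a spending function defined on information time. Table 6 is an empty shell, placed in 9.3 to show that the primary comparison is not split by fluid epoch. Stage-wise ordering is one of several acceptable methods after sequential monitoring.

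All of that stands. It does not supply the missing link from SAP 5 to the boundary. Nor does it answer the estimation point: the estimator and interval as described make no allowance for stopping, so following them gives a biased estimate after an early efficacy stop and an interval that can disagree with the boundary.

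**Conclusion.** The concern holds as a gap between the SAP and the protocol and as an omission in the planned estimation. It is not a fault in the design's error control. On testing the consequence is small: at most about 0.3 percentage points of type I error, and 0.03 points of interval half-width at the final look. On estimation it matters more, and mainly after an early efficacy stop, where the raw difference averages about 6.0 points for a true 4.5, or about 5.7 for a true 3.0. Averaged over all trials, the loss of coverage is one to two percentage points.

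These figures assume looks at 773, 1547 and 2320, 15% mortality in the liberal arm, a normal approximation and no loss to follow-up. The 3.0-point scenario is an illustration chosen for this review, not a figure from the plan. This is a cheap improvement.

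**What to change.** - **SAP 5, Primary Outcome:** state that superiority is judged against the protocol 9.1 efficacy boundary, recomputed from the t^4 spending function at the actual information fractions, and that this is two-sided 0.0472 at the final look if the looks fall as planned. Cite protocol 9.1 directly.
- **Protocol Table 6 and the matching SAP text:** beside the unadjusted values, report a p-value, difference and 95% CI that account for the sequential design, and name the method in advance. Stage-wise ordering with a median-unbiased estimate is one standard choice.

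The cost is a few sentences and a routine calculation. The downside is a slightly wider interval, and a less extreme estimate if the trial stops early. Sample size, boundaries and trial conduct do not change.
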